## **4.3 Rationale for choice of control drugs (comparator/placebo) or combination drugs**

A reference cohort of participants on Injectable Disease Modifying Therapy (iDMT) is included. Permitted iDMTs include interferon or glatiramer acetate. In a prior study, interferon and glatiramer acetate have been found to preserve vaccine responses ([Olberg et al 2018](#)).

## **4.4 Purpose and timing of interim analyses**

For the purpose of early dissemination of results, an interim analysis will be performed once Cohorts 2 and 4 in combination have at least 10 patients enrolled that have had their serum drawn  $\geq$  14 days after full vaccination (two dose) course.

A second interim analysis will be performed once Cohort 6 has at least 10 participants. A third interim analysis will be performed once Cohorts 2-5 have full enrollment with blood drawn  $\geq$  14 days after full course (two doses) vaccination.

## **4.5 Risks and benefits**

There is no benefit expected for participants in this study. Their participation will help contribute to a better understanding of the immune response that occurs when participants receiving ofatumumab are given a COVID-19 mRNA vaccine.

The risk to participants in this trial may be minimized by compliance with the eligibility criteria and study procedures, close clinical monitoring, avoidance of prohibited treatments and adherence to investigator guidance regarding specific safety areas. For further details about ofatumumab, please refer to the Investigator's Brochure (IB) and USPI.

Ofatumumab is approved for the treatment of RMS in several countries. Over 1500 RMS participants have been exposed to ofatumumab across phase 2 and phase 3 studies. In the

pivotal Phase 3 studies COMB157G2301 and COMB157G2302, treatment with ofatumumab significantly lowered the annualized relapse rate (ARR; primary endpoint) compared to the active comparator teriflunomide by >50%. Ofatumumab also significantly reduced the risk of disability progression by >30% and showed significant suppression of both gadolinium (Gd)-enhancing T1 lesions (>90%) and new/enlarging T2 lesions (>80%) on brain MRI compared to teriflunomide.

The data from the ofatumumab program in MS indicates ofatumumab to have an acceptable safety profile and to be well tolerated at the recommended subcutaneous dose of 20 mg. Adverse reactions in the MS population included upper respiratory tract infections, decreased immunoglobulin M, injection site reaction, and injection related reactions. For further details about ofatumumab, please refer to the IB and USPI.

Overall, the balance of benefit and risk supports the proposed clinical study to evaluate the potential of ofatumumab s.c as an effective and safe therapy to address the unmet medical need of participants with RMS.

Women of child-bearing potential must be informed that taking the study treatment may involve unknown risks to the fetus if pregnancy were to occur during the study, and agree that in order to participate in the study they must adhere to the contraception requirements outlined in the exclusion criteria. If there is any question that the participant will not reliably comply, they should not be entered or continue in the study.

Novartis will supply participants in Cohort 1 with ofatumumab treatment as per the assessment schedules in [Table 8-1](#) and [Table 8-2](#).

In the context of the COVID-19 pandemic, additional risks for participants taking part in any clinical trial cannot be excluded. Eligibility criteria for the study requires the Investigator to evaluate infections and exclude participants with ongoing infection. Additionally, this protocol includes home visits (Cohort 1 only) to minimize unnecessary risk that would be associated with on-site visits. Other options like home nursing visits conducted by an off-site healthcare professional and shipment of IMP directly to participants' home may be considered on a case-by-case basis.

#### **4.5.1 Blood sample volume**

Timings of blood sample collection are outlined in the assessment schedules ([Table 8-1](#), [Table 8-2](#), [Table 8-3](#), [Table 8-4](#), [Table 8-5](#) and [Table 8-6](#)).

#### **4.6 Rationale for Public Health Emergency mitigation procedures**

During a Public Health emergency as declared by Local or Regional authorities i.e. pandemic, epidemic or natural disaster, mitigation procedures to ensure participant safety and trial integrity are listed in relevant sections. Notification of the Public health emergency should be discussed with Novartis prior to implementation of mitigation procedures, and permitted/approved by Local or Regional Health Authorities and Ethics Committees as appropriate.

## 5 Study Population

The study population will consist of male and female participants,  $\geq 18$  years of age to 55 years of age inclusive, with a diagnosis of relapsing MS.

The study aims to enroll up to 88 participants at up to 30 centers in the United States. Since a 25% screen failure rate is expected, approximately 117 participants will be screened. 22 participants will be enrolled in Cohort 1. In combination, 22 participants will be enrolled in Cohorts 2 and 4. In combination, 22 patients will be enrolled in Cohorts 3 and 5. In Cohort 6, 22 participants will be enrolled.

### 5.1 Inclusion criteria

Participants eligible for inclusion in Cohort 1 of this study must meet **all** of the following criteria:

1. Signed informed consent must be obtained prior to participation in the study
2. Age 18-55 years old inclusive at Screening
3. Diagnosis of relapsing MS by 2017 revised McDonald criteria
4. Must be willing to comply with the study schedule
5. Will be receiving an mRNA COVID-19 vaccine (Pfizer or Moderna vaccine) at least two weeks prior to starting ofatumumab
6. Eligible to receive and plan to be started on ofatumumab according to the approved labeling
7. Pre-ofatumumab serology with Hepatitis B testing not indicative of active or latent infection
8. Total serum immunoglobulin IgG  $\geq 400$  mg/dl at Screening

Participants eligible for inclusion in Cohort 2 of this study must meet **all** of the following criteria:

1. Signed informed consent must be obtained prior to participation in the study
2. Age 18-55 years old inclusive at Screening
3. Diagnosis of relapsing MS by 2017 revised McDonald criteria
4. Must be willing to comply with the study schedule
5. Will be receiving an mRNA COVID-19 vaccine (Pfizer or Moderna vaccine)
6. Currently on commercially prescribed ofatumumab for  $\geq 4$  weeks for the treatment of RMS
7. Pre-ofatumumab serology with Hepatitis B testing not indicative of active or latent infection
8. Total serum immunoglobulin IgG  $\geq 400$  mg/dl at Screening

Participants eligible for inclusion in Cohort 3 of this study must meet **all** of the following criteria:

1. Signed informed consent must be obtained prior to participation in the study
2. Age 18-55 years old inclusive at Screening
3. Diagnosis of relapsing MS by 2017 revised McDonald criteria

4. Must be willing to comply with the study schedule
5. Will be receiving an mRNA COVID-19 vaccine (Pfizer or Moderna vaccine)
6. Currently on commercially prescribed interferon or glatiramer acetate for  $\geq 4$  weeks for the treatment of RMS
7. Total serum immunoglobulin IgG  $\geq 400$ mg/dl at Screening

Participants eligible for inclusion in Cohort 4 of this study must meet **all** of the following criteria:

1. Signed informed consent must be obtained prior to participation in the study
2. Age 18-55 years old at Screening
3. Diagnosis of relapsing MS by 2017 revised McDonald criteria
4. Must be willing to comply with the study schedule
5. Completed a full course (two doses) of a COVID-19 mRNA vaccine at least  $\geq 4$  weeks after start of commercially prescribed ofatumumab for the treatment of RMS
6. Currently on commercially prescribed ofatumumab for  $\geq 4$  weeks for the treatment of RMS
7. Received two dose mRNA COVID-19 vaccine (Pfizer or Moderna vaccine)  $\geq 2$  weeks ago
8. Pre-ofatumumab serologies with Hepatitis B testing not indicative of active or latent infection
9. Total serum immunoglobulin IgG  $\geq 400$  mg/dl at Screening

Patients eligible for inclusion in Cohort 5 of this study must meet **all** of the following criteria:

1. Signed informed consent must be obtained prior to participation in the study
2. Age 18-55 years old at Screening
3. Diagnosis of relapsing MS by 2017 revised McDonald criteria
4. Must be willing to comply with the study schedule
5. Currently on commercially prescribed interferon or glatiramer acetate for  $\geq 4$  weeks for the treatment of RMS
6. Completed a full course (two doses) of a COVID-19 mRNA vaccine after start of glatiramer acetate or interferon
7. Received two dose mRNA COVID-19 vaccine (Pfizer or Moderna vaccine)  $\geq 2$  weeks ago
8. If the patient has received the mRNA booster, then the mRNA booster should be  $\geq 2$  weeks prior to enrollment.
9. Total serum immunoglobulin IgG  $\geq 400$  mg/dl at Screening

Patients eligible for inclusion in Cohort 6 of this study must meet **all** of the following criteria:

1. Signed informed consent must be obtained prior to participation in the study
2. Age 18-55 years old at Screening
3. Diagnosis of relapsing MS by 2017 revised McDonald criteria
4. Must be willing to comply with the study schedule
5. Currently on commercially prescribed ofatumumab for  $\geq 4$  weeks for the treatment of RMS

6. Completed a full course (two doses) of a COVID-19 mRNA vaccine at least  $\geq$  4 weeks after start of commercially prescribed ofatumumab for the treatment of RMS
7. Received two dose mRNA COVID-19 vaccine (Pfizer or Moderna vaccine)  $\geq$  2 weeks ago
8. Pre-ofatumumab serologies with Hepatitis B testing not indicative of active or latent infection
9. Total serum immunoglobulin IgG  $\geq$  400 mg/dl at Screening
10. Has received an mRNA booster  $\geq$  2 weeks prior to enrollment

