## 2.1 Primary estimands

The estimand is the precise description of the treatment effect and reflects strategies to address events occurring during the trial conduct which could impact the interpretation of the trial results (e.g., premature discontinuation of treatment).

The primary clinical question of interest is: Do relapsing MS participants who receive ofatumumab treatment mount an immune response to non-live mRNA COVID-19 vaccine?

The justification for the primary estimand is that it will capture whether ofatumumab treated participants generate antibodies to mRNA COVID-19 vaccines.

The primary estimand is described by the following attributes:

- **Population:** Defined through appropriate inclusion/exclusion criteria to reflect the targeted population. Relapsing MS participants subdivided into 6 cohorts. (1) Will receive a full course (two doses) of a COVID-19 mRNA vaccine two weeks prior to starting ofatumumab 20 mg subcutaneous treatment; (2) Will receive a full course (two doses) of a COVID-19 mRNA vaccine after at least 4 weeks of commercial ofatumumab 20 mg subcutaneous treatment (3) Will receive a full course (two doses) of a COVID-19 mRNA vaccine after at least 4 weeks of interferon or glatiramer acetate treatment (4) Completed a full course (two doses) of a COVID-19 mRNA vaccine after at least 4 weeks of commercial ofatumumab 20 mg subcutaneous treatment but has not yet received a COVID-19 mRNA booster (5) Completed a full course (two doses) of a COVID-19 mRNA vaccine after at least 4 weeks of interferon or glatiramer acetate (may or may not have received at least 1 COVID-19 mRNA booster) (6) Completed a full course (two doses) of a COVID-19 mRNA vaccine after at least 4 weeks of commercial ofatumumab 20 mg subcutaneous treatment and received at least 1 additional booster vaccine  $\geq$  14 days prior to Screening.
- **Variable:** Achieving immune response as defined by a positive SARS-CoV-2 qualitative IgG antibody assay  $\geq$  14 days after full course (two doses) vaccination (yes/no)
- **Treatment of interest:** Non-live COVID-19 mRNA vaccine either two weeks prior to ofatumumab start or at least 4 weeks after ofatumumab start or while on interferon or glatiramer acetate
- **Intercurrent event:** Discontinuation of treatment/study, or death
- **Summary measure:** Proportion of participants achieving immune response

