##### Cohort 1:

For participants who receive the Pfizer vaccine, the first of three 20 mg s.c ofatumumab loading doses will be administered on Day 36 or 2 weeks after receiving a full course (two doses) of a COVID-19 vaccine. The 2nd and 3rd loading doses should be administered on Day 43 and Day 50 or 7 and 14 days respectively after the 1st loading dose. Subsequent dosing includes 20 mg s.c. administered monthly starting at Day 64.

For participants who receive the Moderna vaccine, the first of three 20 mg s.c ofatumumab loading doses will be administered on Day 43 or 2 weeks after receiving a full course (two doses) of a COVID-19 vaccine. The 2nd and 3rd loading doses should be administered on Day 50 and Day 57 or 7 and 14 days respectively after the 1st loading dose. Subsequent dosing includes 20 mg s.c administered monthly starting at Day 71.

**Cohort 2:** Will continue taking their prescribed ofatumumab as per their current dosing schedule.

**Cohort 3:** Will continue administration of their prescribed interferon or glatiramer acetate as per their current dosing schedule.

[figure not shown]
**Cohort 4:** Will continue taking their prescribed ofatumumab as per their current dosing schedule and should adhere to the visit schedule as shown in either [Table 8-5](#) (Pfizer) or [Table 8-6](#) (Moderna).

**Cohort 5:** Will continue taking their prescribed glatiramer acetate or interferon as per their current dosing schedule and should adhere to the visit schedule as shown in either [Table 8-5](#) (Pfizer) or [Table 8-6](#) (Moderna).

[figure not shown]
**Cohort 6:** Will continue taking their prescribed ofatumumab as per their current dosing schedule and should adhere to the visit schedule as shown in either [Table 8-5](#) (Pfizer) or [Table 8-6](#) (Moderna).

[figure not shown]
Study design schematics for Cohorts 1, 2 and 3 are shown in [Figure 3-1](#), [Figure 3-2](#), [Figure 3-3](#), and [Figure 3-4](#). Study design schemas for Cohorts 4, 5, and 6 are shown in [Figure 3-5](#) and [Figure 3-6](#).

[figure not shown]
[figure not shown]
[figure not shown]

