### **6.1.3 Treatment cohorts**

- Cohort 1: RMS participants receiving non-live COVID-19 mRNA vaccine at least two weeks prior to ofatumumab start.
- Cohort 2: RMS participants receiving non-live COVID-19 mRNA vaccine at least 4 weeks after ofatumumab start.
- Cohort 3: RMS participants receiving non-live COVID-19 mRNA vaccine at least 4 weeks after start of prescribed interferon or glatiramer acetate.
- Cohort 4: RMS participants having completed a full course (2 doses) of a non-live COVID-19 mRNA vaccine  $\geq$  4 weeks after ofatumumab start.
- Cohort 5: RMS participants having completed a full course (2 doses) of a non-live COVID-19 mRNA vaccine  $\geq$  4 weeks after glatiramer acetate or interferon start.
- Cohort 6: RMS participants having completed a full course (2 doses) of a non-live COVID-19 mRNA vaccine  $\geq$  4 weeks after ofatumumab start and having received a booster  $\geq$  14 days prior to screening

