## **12 Data analysis and statistical methods**

The analysis will be conducted on all participant data at the time the trial ends. Any data analysis carried out independently by the investigator should be submitted to Novartis prior to publication or presentation.

Categorical variables will be presented as counts and percentages. For continuous variable, mean, standard deviation, minimum, 25th percentile, median, 75th percentile, and maximum will be presented. All summaries will be presented for Cohort 1, Cohorts 2 and 4, Cohorts 3 and 5, and Cohort 6.

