2.4 Treatments (study treatment, rescue medication, concomitant therapies, compliance)

2.4.1 Study treatment / compliance

Participants in all cohorts must intend to receive or have received both doses of a COVID-19 mRNA vaccine.

The following variables will be summarized descriptively as continuous variables by cohort group unless otherwise specified:

- Time (days) from first dose of ofatumumab to last dose of ofatumumab for Cohort 1 participants
- Time (days) from first dose of earliest MS DMT to:
 - first dose of COVID-19 vaccine
 - primary analysis time point (see [Section 1.1](#))
- Time (days) from first dose of most recent MS DMT to:
 - first dose of COVID-19 vaccine
 - primary analysis time point (see [Section 1.1](#))

MS treatment compliance will be listed by individual cohort and participant.

Study duration

Study duration in days will be calculated as [(date of last contact/EOS – date of Visit 1) + 1] and summarized descriptively as a continuous variable by cohort group.

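### Cohorts 4 and 6 tie the 4 weeks on ofatumumab to completion of the vaccine course and leave dose 1 unconstrained, so some participants may be primed outside the stated treatment of interest

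*Protocol*

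**What the plan says.** Protocol 5.1, Cohort 4 item 5 and Cohort 6 item 6, require "Completed a full course (two doses) of a COVID-19 mRNA vaccine at least" 4 "weeks after start of commercially prescribed ofatumumab for the treatment of RMS". The Protocol summary, Protocol 2.1 (population) and 6.1.3, and SAP 1.1, 1.2.1 and 2.5.1 also describe these cohorts by completion of the course. Both cohorts were vaccinated before enrolment. No section sets a condition on their dose 1 or a maximum interval between their doses.

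The treatment of interest in Protocol 2.1 is "Non-live COVID-19 mRNA vaccine either two weeks prior to ofatumumab start or at least 4 weeks after ofatumumab start", or vaccine while on a comparator drug. Protocol 6.1.3 describes the vaccine-naive ofatumumab group as "Cohort 2: RMS participants receiving non-live COVID-19 mRNA vaccine at least 4 weeks after ofatumumab start".

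On presentation, Protocol 12 states: "All summaries will be presented for Cohort 1, Cohorts 2 and 4, Cohorts 3 and 5, and Cohort 6". SAP 2.1 uses the same groups. SAP 2.4.1 summarises the time from the first dose of the earliest, and of the most recent, MS disease-modifying therapy (DMT) to "first dose of COVID-19 vaccine". The SAP plans no subgroup analysis (2.2.1), no sensitivity analysis of the primary endpoint (2.5.5) and no exclusion rule for analysis sets (5.5).

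**The concern.** Cohorts 2+4 and Cohort 6 answer the second question in Protocol 4.1: can participants respond when vaccinated after ofatumumab has been introduced? If the 4 weeks applies only to dose 2, part of the course may have been given during the first weeks of ofatumumab. Such a participant does not clearly meet the treatment of interest but counts in the on-ofatumumab response rate.

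The pooled Cohort 2+4 group could then mix two exposure conditions, one with both doses after at least 4 weeks on drug and one with only dose 2 guaranteed to be. Protocol 1.1 gives diminished vaccine response under anti-CD20 therapy as the reason for the study. If that premise is right, early priming would plausibly raise the estimate. No planned analysis separates these participants.

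**Working it through.** **The plan's own figure.** The sample-size sections state half-widths of 20.1%, 19% and 17.5% for n = 20 at response rates of 70%, 75% and 80%. The Wald formula 1.96 × √(p(1−p)/20) gives 20.08%, 18.98% and 17.53%, so they reproduce. The point does not depend on them; they serve as a yardstick below.

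**Dose intervals.** In the Cohort 1 text of Protocol 3, first ofatumumab for Pfizer "will be administered on Day 36 or 2 weeks after receiving a full course (two doses) of a COVID-19 vaccine", and for Moderna "will be administered on Day 43 or 2 weeks after receiving a full course (two doses) of a COVID-19 vaccine".
- Pfizer: dose 2 on Day 36 − 14 = Day 22; interval 22 − 1 = 21 days.
- Moderna: dose 2 on Day 43 − 14 = Day 29; interval 29 − 1 = 28 days.

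The visit days in Tables 8-1 to 8-4 agree.

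**Earliest dose 1 in Cohorts 4 and 6, read literally.** Set ofatumumab start as day 0 and require only dose 2 ≥ day 28. Earliest dose 1 = 28 − interval.
- Pfizer: 28 − 21 = day 7.
- Moderna: 28 − 28 = day 0.
- Dose 2 delayed: a 35-day interval gives day −7 and a 42-day interval gives day −14. Dose 1 precedes ofatumumab only if the interval exceeds 28 days.

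The Cohort 1 dosing days 36, 43, 50 and 64 correspond to days 0, 7, 14 and 28 from start, so an eligible dose 1 can fall within the loading phase.

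**Cohort 2.** Item 6 requires at least 4 weeks on ofatumumab at entry, and Protocol 8 places Visits 2 and 3 before vaccination.
- Dose 1: day 28 or later.
- Dose 2: 28 + 21 = day 49 or later (Pfizer), or 28 + 28 = day 56 or later (Moderna).

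**Who is affected.** With on-schedule dosing, dose 1 falls before day 28 only if dose 2 falls on days 28 to 48 (Pfizer) or 28 to 55 (Moderna). The documents do not say how many participants this describes.

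**Scale, on assumed values.** If k of 22 participants in a group were primed early and their true response rate were d higher, the group rate rises by (k/22) × d.

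| k | d = 0.10 | d = 0.30 | d = 0.50 |
|---|---|---|---|
| 1 | 0.5 points | 1.4 | 2.3 |
| 2 | 0.9 | 2.7 | 4.5 |
| 4 | 1.8 | 5.5 | 9.1 |

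Both k and d are assumptions; the documents give neither.

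**The case against.** The criterion can be read another way: that the whole course followed at least 4 weeks of drug. Protocol 2.1 gives this some support, because it describes Cohorts 2 and 4 in nearly the same phrase with only the tense changed. The treatment of interest does not name a dose either. This objection stands in part. The literal text tests completion, nothing excludes that reading, and up to 30 centers must apply it, so the wording needs reconciling. The documents do not show that sites used the date of dose 2.

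A reader might infer that Cohorts 4 and 6 count people primed at or before ofatumumab start as vaccinated on drug. The documents do not support that as a general statement. On schedule, Pfizer dose 1 cannot precede day 7, and Moderna dose 1 reaches day 0 only if dose 2 falls exactly on day 28. Priming before start needs a dose interval above 28 days, which is neither excluded nor reported.

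A reader might also infer an established bias in favour of ofatumumab. Its direction depends on early-primed participants responding better, and its size on two unknown quantities. In Cohort 6 the primary assay follows a booster (SAP 2.4.1.1), which would dilute any effect of early priming.

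Three practical points also carry weight. No hypothesis is tested. The illustrated shifts are smaller than the stated margins of 17.5 to 20.1 points. SAP 2.4.1 would show some of the timing descriptively, and all data are listed. But a summary of intervals does not show how the response rate changes without these participants. The "earliest" DMT interval may also start from a different, previous drug.

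**Conclusion.** The point holds as an ambiguity with a possible effect on the estimate. As worded, the criterion can admit participants to Cohorts 4 and 6 whose dose 1 came less than 4 weeks after ofatumumab start, whereas Cohort 2 cannot include them. No planned analysis isolates them.

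The timing limits (day 7 Pfizer, day 0 Moderna, against day 28 in Cohort 2) follow from the protocol's own schedule and the literal reading. An upward bias in Cohorts 2+4, and a smaller one in Cohort 6, is conditional on better response in early-primed participants. Its size cannot be computed from the documents. One participant is 1/22 = 4.5% of a full group, so even a few could move the rate by some points. This is worth correcting because the correction is cheap, but it does not undermine the study.

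**What to change.** 1. Reconcile Protocol 2.1, 5.1 and 6.1.3 with SAP 1.1, 1.2.1 and 2.5.1, so that all state which dose the 4 weeks refers to. Which dose is meant is for the sponsor to settle.
2. In SAP 2.5.6, add a supplementary row with the Cohort 2+4 and Cohort 6 response rates and exact confidence intervals, restricted to participants whose dose 1 was at least 28 days after the start of ofatumumab. Report how many are excluded from each group.
3. Measure that interval from the start of ofatumumab itself, not from the "earliest" MS DMT. An earlier drug could otherwise make a participant appear to qualify.

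This uses dates that the SAP 2.4.1 summaries already need and leaves the sample size unchanged. The current SAP amendment is dated before database lock, so the row could be specified even if enrolment is complete. The cost is one extra row with a slightly smaller n and a wider interval. For scale, at a 75% response rate the Wald half-width 1.96 × √(0.75 × 0.25/n) is 18.1% with 22 participants, 19.0% with 20 and 20.0% with 18.

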Study design	
This is a 6-cohort, multicenter, prospective study of up to 88 relapsing MS participants.
 
  
 Cohort	Brief Description	
   
 1	Vaccine naive, planning to start OMB	
 
 2	Vaccine naive, currently on OMB for <math>\geq</math> 4 weeks	
 
 3	Vaccine naive, on interferon or glatiramer acetate for <math>\geq</math> 4 weeks	
 
 4	Fully vaccinated, currently on OMB for <math>\geq</math> 4 weeks	
 
 5	Fully vaccinated, on interferon or glatiramer acetate for <math>\geq</math> 4 weeks, +/- booster	
 
 6	Fully vaccinated, currently on OMB for <math>\geq</math> 4 weeks, + booster	
  
 
All groups will undergo serologic testing.
 
Participants will obtain the COVID-19 mRNA vaccine from their HCP (private insurance) or appropriate federal, state or local program.
	Cohort	Brief Description	1	Vaccine naive, planning to start OMB	2	Vaccine naive, currently on OMB for $\geq$ 4 weeks	3	Vaccine naive, on interferon or glatiramer acetate for $\geq$ 4 weeks	4	Fully vaccinated, currently on OMB for $\geq$ 4 weeks	5	Fully vaccinated, on interferon or glatiramer acetate for $\geq$ 4 weeks, +/- booster	6	Fully vaccinated, currently on OMB for $\geq$ 4 weeks, + booster
Cohort	Brief Description														
1	Vaccine naive, planning to start OMB														
2	Vaccine naive, currently on OMB for $\geq$ 4 weeks														
3	Vaccine naive, on interferon or glatiramer acetate for $\geq$ 4 weeks														
4	Fully vaccinated, currently on OMB for $\geq$ 4 weeks														
5	Fully vaccinated, on interferon or glatiramer acetate for $\geq$ 4 weeks, +/- booster														
6	Fully vaccinated, currently on OMB for $\geq$ 4 weeks, + booster														
Study population	Adult (ages 18-55) relapsing MS participants														
Key Inclusion criteria	
Patients eligible for inclusion in Cohort 1 of this study must fulfill the following criteria:
 
 
1. Signed informed consent must be obtained prior to participation in the study
 
2. Age 18-55 years old inclusive at Screening
 
3. Diagnosis of relapsing MS by 2017 revised McDonald criteria
 
4. Must be willing to comply with the study schedule
 
														

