## 5.2 Exclusion criteria

Participants meeting any of the following criteria are not eligible for inclusion in this study:

1. Already has received the J&J vaccine.
2. Has a contraindication to receiving an mRNA COVID-19 vaccine
3. Has an immediate allergic reaction to past vaccine or injection
4. Any safety finding including low immunoglobulin IgG and/or low immunoglobulin IgM levels requiring an ofatumumab treatment interruption within the 12 weeks immediately prior to vaccination as determined by the HCP
5. Any major episode of infection requiring hospitalization or treatment with intravenous antibiotics within 4 weeks prior to the first vaccination visit or oral antibiotics within two weeks prior to the first vaccination visit
6. Prior treatment with B-cell targeted therapies (e.g., rituximab or ocrelizumab), alemtuzumab, anti-CD4, cladribine, cyclophosphamide, mitoxantrone, azathioprine, mycophenolate mofetil, cyclosporine, methotrexate, total body irradiation, or bone marrow transplantation
7. Prior treatment with S1P agent within 2 months at Screening
8. Prior treatment with natalizumab within 6 months of study enrollment
9. Since commercially prescribed ofatumumab is being used in the study, contraindications as per the USPI will be adhered to which include active infection hepatitis B infection, progressive multifocal leukoencephalopathy and pregnancy.
10. Participation in another interventional clinical trial within 14 days before enrollment.
11. Use of other investigational drugs at the time of enrollment (Screening) or within the prior 30 days, or five elimination half-lives, or until the expected pharmacodynamic effect has returned to baseline, whichever is longer.
12. History of hypersensitivity to any of the study treatments or its excipients or to drugs of similar chemical classes.
13. Have been treated with any of the medications listed below within the time specified:

Medication	Exclusionary if used within the timeframe specified below
Intravenous, oral, intra-articular or intramuscular corticosteroids, adrenocorticotropic hormone	30 days prior to Screening

Medication	Exclusionary if used within the timeframe specified below
Immunosuppressive, chemotherapeutic medications (e.g. mitoxantrone, cyclophosphamide, cladribine, S1P modulators)	2 months prior to first study drug administration
Natalizumab	Within 6 months of study enrollment/Visit 2

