#### **6.4.1.1 Treatment assignment, randomization**

No randomization will be performed in this study. The assignment of a participant to a cohort will be determined by inclusion/exclusion criteria.

An IRT system will be used to track participant visits and status. IRT will also be used to dispense treatment to Cohort 1 as indicated in the assessment schedules in [Table 8-1](#) and [Table 8-2](#).

At dosing visits, the system will specify unique medication numbers that will correspond to open-label treatment to be dispensed.

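### Cohort 4's entry criteria omit the no-booster condition that defines the cohort, and the SAP's booster analyses would miss a Cohort 4 participant boosted before entry

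*Protocol*

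**What the plan says.** Protocol 6.4.1.1 states that there is no randomization and that "The assignment of a participant to a cohort will be determined by inclusion/exclusion criteria".

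Protocol 2.1 describes the Cohort 4 population as patients who completed two mRNA doses after at least 4 weeks of ofatumumab "but has not yet received a COVID-19 mRNA booster". SAP 1.2.1 and 2.5.1 repeat this condition.

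In Protocol 5.1, Cohort 4 has two vaccination criteria. The first begins "Completed a full course (two doses) of a COVID-19 mRNA vaccine at least" and refers to the start of ofatumumab. The second requires that the two-dose vaccine was received at least 2 weeks ago. Neither mentions a booster, and the key criteria in the Protocol summary are equally silent. Cohort 5 has a criterion on the timing of any booster, and Cohort 6 has one that requires a booster. The only exclusion in Protocol 5.2 that concerns an earlier COVID-19 vaccination is "Already has received the J&J vaccine".

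On analysis, Protocol 12 and SAP 2.1 pool Cohort 4 with Cohort 2 and keep Cohort 6 separate. SAP 1.1 sets the primary time point for Cohorts 4 to 6 at Visit 2. SAP 2.4.1.1, Table 8, sets the vaccine day to the second dose for Cohorts 4 and 5 and to the booster for Cohort 6. Protocol 12.5 foresees participants enrolled after one or more boosters and says they will be segregated for further analysis. SAP 2.5.6 and 2.6.6 define the booster analyses as Cohort 6 plus participants in Cohorts 1 to 5 who are boosted while in the study.

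**The concern.** If the criteria decide the cohort, they have to separate the cohorts. Here they do not separate an unboosted ofatumumab patient (Cohort 4) from a boosted one (Cohort 6), yet the two are reported in different groups. A boosted patient placed in Cohort 4 would supply a post-booster sample that is counted as a response to two doses.

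This bears on the second aim in Protocol 1.2, the effect of a booster on immune response. Among ofatumumab-treated participants, the descriptive comparison that addresses it is Cohorts 2 and 4 against Cohort 6. If boosters raise response, misplacement acts in one direction: the two-dose rate goes up and the apparent booster effect shrinks. A confidence interval does not reflect an error of this kind.

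**Working it through.** **1. Criteria side by side (Protocol 5.1).**

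| Condition | Cohort 4 | Cohort 6 |
|---|---|---|
| Consent, age, diagnosis, willingness | yes | yes |
| Two doses completed at least 4 weeks after ofatumumab start | yes | yes |
| On ofatumumab for at least 4 weeks | yes | yes |
| Two-dose vaccine at least 2 weeks ago | yes | yes |
| Hepatitis B serology; IgG at least 400 mg/dl | yes | yes |
| Booster at least 2 weeks before enrollment | not mentioned | required |
| No booster | not mentioned | does not apply |

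Cohort 6 is Cohort 4's nine criteria plus one. Two consequences follow:
- Every patient eligible for Cohort 6 is also eligible for Cohort 4.
- A patient boosted less than 2 weeks before enrollment fails Cohort 6 but still meets every Cohort 4 criterion.

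**2. Following a Cohort 4 participant boosted before entry through the SAP.**
- Group: Cohorts 2 and 4 combined (SAP 2.1, 2.5.2).
- Sample: Visit 2, with the vaccine day set to dose 2 (SAP 1.1; 2.4.1.1, Table 8). The booster date plays no part.
- Booster analyses: not included, because the participant is neither in Cohort 6 nor boosted while in the study (SAP 2.5.6, 2.6.6).
- Immune conversion: Table 1 of the SAP limits the nucleocapsid-based definition to unboosted participants, but SAP 2.6.1 applies it to Cohorts 4 and 5 by cohort label.

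Protocol 12.5 says such participants will be segregated. No SAP analysis does this, and SAP Section 4 declares no changes to the protocol-specified analyses.

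**3. The plan's own precision figures.** Half-width = 1.96 × √(p(1 − p)/20):
- p = 0.70: 20.08 points (stated 20.1)
- p = 0.75: 18.98 points (stated 19)
- p = 0.80: 17.53 points (stated 17.5)

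These reproduce. With the exact interval that the plan will use, the half-widths at 14/20, 15/20 and 16/20 are 21.2, 20.2 and 19.0 points.

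**4. Illustrative size.** The documents give neither response rates by booster status nor a number of misplaced participants, so both are assumed. If k of the 22 in Cohorts 2 and 4 are already boosted and respond d points more often, the group rate shifts by (k/22) × d.

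| k | d = 20 | d = 30 |
|---|---|---|
| 2 | 1.8 | 2.7 |
| 4 | 3.6 | 5.5 |
| 5 | 4.5 | 6.8 |
| 6 | 5.5 | 8.2 |

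For example, with 60% after two doses and 90% after a booster:
- k = 2: (20 × 60 + 2 × 90)/22 = 62.7%
- k = 5: (17 × 60 + 5 × 90)/22 = 66.8%

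The difference from Cohort 6 then falls from 30 points to 27.3 and 23.2 points.

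**The case against.** The intent is clear. The estimand says Cohort 4 is unboosted, the SAP repeats it, and the cohort table in the Protocol summary marks boosters for Cohorts 5 and 6 and not for Cohort 4. A boosted ofatumumab patient has a cohort made for that situation, with its own 22 places, so a site would have to overlook these definitions to go wrong. The illustrative shift is well inside the planned half-width of 17.5 to 20.1 points, no hypothesis is tested, and no formal comparison with Cohort 6 is specified.

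Most of this stands as a reason to expect few cases. It does not remove the contradiction: the protocol names the criteria as the assignment rule, and the criteria lack the condition. Nor does it help a patient boosted less than 2 weeks before enrollment, for whom Cohort 6 is closed and Cohort 4 is open. Protocol 12.5 shows that boosted entrants were foreseen, but the SAP does not carry the promise through.

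A reader might go further and infer that Cohorts 1 to 3 are equally exposed. The summary describes them as "Vaccine naive, planning to start OMB", "Vaccine naive, currently on OMB for" at least 4 weeks and "Vaccine naive, on interferon or glatiramer acetate for" at least 4 weeks. The Cohort 1 criterion reads "Will be receiving an mRNA COVID-19 vaccine (Pfizer or Moderna vaccine) at least two weeks prior to starting ofatumumab", those for Cohorts 2 and 3 ask only for a future mRNA vaccine, and prior mRNA doses are not excluded. The wording gap exists, but the documents do not support treating it as an equal threat:
- The estimand requires a full two-dose course still to come.
- Section 8 schedules visits around the first and second doses.
- Section 9.1.2 requires discontinuation if the course is not completed.
- Antibody is measured before vaccination, at Screening for Cohort 1 (Table 8-1) and at Visit 2 for Cohorts 2 and 3 (Tables 8-3 and 8-4).

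Someone already vaccinated and awaiting a single further dose does not fit that scheme.

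**Conclusion.** The point holds for Cohort 4. The entry criteria contradict the estimand population they are meant to produce, and the SAP neither detects nor separates a Cohort 4 participant boosted before entry, contrary to Protocol 12.5. It should be corrected, though it does not undermine the design.

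The shift of about 3 to 7 points for 2 to 5 of 22 participants is illustrative. It rests on an assumed 30-point higher response after a booster and an assumed number of cases. A reader might infer that boosted participants were in fact placed in Cohort 4; nothing in the documents shows this. For Cohorts 1 to 3 the mismatch with the vaccine-naive description is a matter of consistency, and misassignment there is unlikely. No sample-size figure changes because of this point.

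**What to change.** **Protocol.** Add to the Cohort 4 criteria, in Section 5.1 and in the summary: *has not received a COVID-19 mRNA booster before enrollment*. This takes over the document's own definition and costs one line.

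**SAP.** The current SAP amendment is dated 28-Jun-2023, before database lock, so a new criterion may come too late for most participants. The derivation below then does the work:
- Derive booster status at the primary time point from documented vaccine dates. For Cohorts 4 to 6 the Vaccine Administration Form is scheduled at Screening (Protocol Tables 8-5 and 8-6); use prior-medication records as well.
- Analyse Cohort 4 participants boosted before entry outside the two-dose group of Cohorts 2 and 4.
- Extend the analyses in SAP 2.5.6 and 2.6.6 to boosters received before or during the study. This also brings in Cohort 5 participants boosted before entry, whom the present wording leaves out.
- Apply the nucleocapsid-based conversion definition by derived booster status, not by cohort label.

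**Secondary edit.** Align the Cohorts 1 to 3 criteria with the vaccine-naive description, and check earlier doses from prior-medication records. Tables 8-1, 8-3 and 8-4 schedule the Vaccine Administration Form only at Visits 2 and 3, so it is not shown to record earlier doses there.

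**Cost.** A short derivation and perhaps a few reassignments; no change to visits or sample size. Moving participants costs some precision. Removing 5 leaves 17, and at a 70% response rate the plan's formula gives 1.96 × √(0.21/17) = 21.8 points, against 20.1 with 20.
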